3.3 DOSE MODIFICATIONS

No dose modifications are allowed for BMS-986253. Dose modifications for toxicity related to the DNMTi used will be done according to standard of care per the FDA product label recommendations.

3.4 EVALUATIONS DURING THE TREATMENT

All evaluation days, for flexibility around participant schedules, can be performed up to +/-3 days. If a participant visit is delayed greater than 3 days due to weather, medical issues, or etc., the next evaluation will occur when possible and the 2 week cycle will reset from that point (the next dose will be 2 weeks +/-3 days from the previous dose).

Phase I and Phase II, C1, C_(1+x) and beyond (until off treatment criteria are met):

- Day 1 – all lab checks and medical evaluation will be done **pre-dose**:
 - History and Physical Exam
 - Vital signs
 - CBC with differential, platelet count, and reticulocyte count
 - Serum chemistry panel (includes sodium, chloride, potassium, CO₂, BUN, Creatinine, glucose, AST/ALT, Alkaline phosphatase, total bilirubin, direct bilirubin, albumin, total protein, magnesium, phosphorous, calcium, LDH, uric acid), CRP
 - Blood type and screen (as clinically indicated)
 - TBNK (CD3, CD4, CD8, CD19 clinical panel)
 - Urinalysis
 - Serum beta-HCG for females of childbearing potential (FCBP) (within 24 hours of Day 1)
 - Blood samples for pharmacokinetics (PK) and pharmacodynamics (PD) (see section **5.1**)
 - For Phase I participants only
 - Transfusion dependency assessment
 - Concomitant medications assessment
 - BMS-986253 administration
- Day 2:
 - Vital signs (only for Cycle 1)

- Clinician assessment (only for Cycle 1)
- Blood samples for 24-hour PK/PD timepoint (see Section 5.1)
- Start oral decitabine and cedazuridine (Day 1 of 5 of DNMTi)
- Days 3-6:
 - DNMTi administration of oral decitabine and cedazuridine (HR-MDS cohorts).
- Day 8:
 - Weekly Labs (only for Cycle 1) CBC/diff, reticulocyte count, chemistries (as above and included CRP)
- Day 15 – all lab checks and medical evaluation will be done pre-dose:
 - History and Physical Exam
 - Vital signs
 - CBC with differential, platelet count, and reticulocyte count
 - Blood type and screen (as clinically indicated)
 - Serum chemistry panel (includes sodium, chloride, potassium, CO2, BUN, Creatinine, glucose, AST/ALT, Alkaline phosphatase, total bilirubin, direct bilirubin, albumin, total protein, magnesium, phosphorous, calcium, LDH, uric acid), CRP
 - TBNK (CD3, CD4, CD8, CD19 clinical panel)
 - Urinalysis
 - Serum beta-HCG for females of childbearing potential (FCBP) (within 24 hours of Day 1)
 - Blood samples for pharmacokinetics (PK) and pharmacodynamics (PD) (see section 5.1)
 - For Phase I participants only
 - Concomitant medications assessment
 - BMS-986253 administration
- Days 16
 - Vital signs (only for Cycle 1)
 - Clinician assessment (only for Cycle 1)
 - Blood samples for 24-hour PK timepoint (see Section 5.1)
- Day 22:
 - Weekly Labs (only for Cycle 1) CBC/diff, reticulocyte count, chemistries (as above including CRP)
- Day 28
 - Bone marrow evaluation (aspiration and biopsy) per protocol or per clinical necessity.
 - Morphology, flow cytometry, cytogenetics, molecular tests, and research - see section 5.1)
 - Per protocol, bone marrow biopsy after initiation of therapy required:
 - Phase I post cycle 1(C1D28 +/- 3 days)

- Phase II post cycle 2 (C2D28 +/- 3 days)
- Phase II post cycle 6 (C6D28 +/- 3 days)
- With development of treatment-related aplasia or concern for disease progression
 - All other BMB are optional and per PI or LAI discretion.
- Peripheral blood flow cytometry (if peripheral blood blasts present, will trend at end of each treatment cycle until clearance)
- Research blood per section **5.1**

AT DISEASE PROGRESSION

If participant has disease progression on treatment while being evaluated at the NIH the following tests will be done within 7 days after diagnosis of progression.

- Research Blood per section **5.1**
- TBNK (CD3, CD4, CD8, CD19 clinical panel)
- Adverse event and transfusion requirement assessment
- Mandatory Bone Marrow Biopsy and aspirate
- Peripheral blood flow cytometry (if evidence of peripheral blood blasts and NGS myeloid mutation panel)
- CBC with differential, platelet count, and reticulocyte count
- Blood type and screen (as clinically indicated)
- Serum chemistry panel (includes sodium, chloride, potassium, CO2, BUN, Creatinine, glucose, AST/ALT, Alkaline phosphatase, total bilirubin, direct bilirubin, albumin, total protein, magnesium, phosphorous, calcium; also need LDH, uric acid, CRP)
- PT/INR, PTT and fibrinogen

END OF TREATMENT VISIT

Will be done 30 ± 7 days from the end of the last cycle on therapy.

- History & Physical Exam
- Vital signs
- Serum beta-HCG for females of childbearing potential (FCBP) Urinalysis
- CBC with differential, platelet count, and reticulocyte count
- Fibrinogen
- Blood type and screen (as clinically indicated)
- Serum chemistry panel (includes sodium, chloride, potassium, CO2, BUN, Creatinine, glucose, AST/ALT, Alkaline phosphatase, total bilirubin, direct bilirubin, albumin, total protein, magnesium, phosphorous, calcium; also need LDH, uric acid, CRP)
- Concomitant medications assessment
- Adverse event and transfusion dependency assessment
- Research blood collection only if bone marrow performed (see section **5.1**)
- TBNK (CD3, CD4, CD8, CD19 clinical panel)
- EORTC (see section **3.5.3**)
- Psychosocial Assessment (see section **3.5.3**)

FOLLOW-UP

After the End of Treatment visit, follow up will occur via phone call every 3 months (+/- 1 month) for first 24 months, then every 6 months (+/- 3 months) at least 5 years post enrollment. . Outside medical records will be requested along with the phone call for the first follow-up visit only.

- Overall survival, event- and progression-free survival status

Adverse events assessment (only at first follow-up visit)

END OF STUDY

- Overall survival, event- and progression-free survival status will be assessed via phone call.

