- l. Follow up will occur via phone call every 3 months (+/- 1 month) for first 24 months, then every 6 months (+/- 3 months)up to 5 years post enrollment. . Outside medical records will be requested along with the phone call for the first follow-up visit only.
- m. Within 7 days
- n. See section **2.2.2**, **2.4**, and **3.4** for detailed lab collection instructions. For Cycle 1, patients will undergo weekly lab monitoring with CBC/diff, and chemistry (see section **3.4**) on days 8 and 22.
- o. Weight only
- p. Rockwood/CFS and MDS-CI to be completed at baseline only; EORTC-QLQC and Psychosocial assessment will be completed per section **3.5.3**. Questionnaires required only in English speaking participants.
- q. See Safety monitoring guidelines during infusion (Section **3.2.1.4.1**)
- r. Response assessment Phase I post cycle 1 and as clinically indicated and Phase 2 post cycle 2, post cycle 6, and as clinically indicated.
- s. Only at first follow up time point; See section **6.1**
- t. See Section **3.2.1.4.1** for details on frequency of vital sign monitoring during first infusion of BMS-986253. Vital signs required for D2 and D16 of Cycle 1 only.

* CFS: Clinical Frailty Scale; MDC-CI: MDS-Specific Comorbidity Index; EORTC-QLQC: European Organization for Research and Treatment of Cancer (EORTC) quality of life questionnaire (QLQ)

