3.8.1 Criteria for removal from protocol therapy

- Progressive disease
- Participant requests to be withdrawn from active therapy
- Unacceptable toxicity as (section 3.3)
- Lack of clinical response seen after 6 cycles of therapy (C7D1)
- Completion of safety visit
- Investigator discretion
- Positive pregnancy test

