6.3.1 Response Criteria

The table below shows the 2006 International Working Group response criteria for altering the natural history of MDS,[\[115\]](#) with modified definitions for HI-E, HI-P, and HI-N in the suggested 2018 International Working Group response criteria.[\[85\]](#)

Category	Response criteria (responses must last at least 4 weeks)
Complete remission	
 • Bone marrow: $\leq 5\%$ myeloblasts with normal maturation of all cell lines* • Persistent dysplasia will be noted* • Peripheral blood† 
 • Hgb ≥ 11 g/dL • Platelets $\geq 100 \times 10^9/L$ • Neutrophils $\geq 1.0 \times 10^9/L$ • Blasts 0%
Partial remission	All CR criteria if abnormal before treatment except: 
 • Bone marrow blasts decreased by $\geq 50\%$ over pretreatment but still $> 5\%$ • Cellularity and morphology not relevant
Marrow CR	
 • Bone marrow: $\leq 5\%$ myeloblasts and decrease by $\geq 50\%$ over pretreatment • Peripheral blood: if HI responses, they will be noted in addition to marrow CR

Stable disease	Failure to achieve at least PR, but no evidence of progression for >8 wks
Failure	Death during treatment or disease progression characterized by worsening of cytopenias, increase in percentage of bone marrow blasts, or progression to more advanced MDS FAB subtype than pre-treatment
Relapse after CR or PR	At least 1 of the following: 
 Return to pre-treatment bone marrow blast percentage Decrement of $\geq 50\%$ from maximum remission/response levels in granulocytes or platelets Reduction in Hgb concentration by ≥ 1.5 g/dL or transfusion dependence
Cytogenetic response	Complete 
 Disappearance of the chromosomal abnormality without appearance of new ones Partial 
 At least 50% reduction of the chromosomal abnormality
Disease progression	For participants with: 
 Less than 5% blasts: $\geq 50\%$ increase in blasts to $>5\%$ blasts 5%-10% blasts: $\geq 50\%$ increase to 10% blasts 10%-20% blasts: $\geq 50\%$ increase to $>20\%$ blasts 20%-30% blasts: $\geq 50\%$ increase to $>30\%$ blasts Any of the following: 
 At least 50% decrement from maximum remission/response in granulocytes or platelets Reduction in Hgb by ≥ 2 g/dL Transfusion dependence

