Survival	Endpoints: 
 Overall: death from any cause Event free: failure or death from any cause PFS: disease progression or death from MDS DFS: time to relapse Cause-specific death: death related to MDS

MDS, myelodysplastic syndromes; Hgb, hemoglobin; CR, complete remission; HI, hematologic improvement; PR, partial remission; FAB, French-American-British; AML, acute myeloid leukemia; PFS, progression-free survival; DFS, disease-free survival.

To convert hemoglobin from grams per deciliter to grams per liter, multiply grams per deciliter by 10.

*Dysplastic changes should consider the normal range of dysplastic changes.

†In some circumstances, protocol therapy may require the initiation of further treatment (eg, consolidation, maintenance) before the 4-week period. Such participants can be included in the response category into which they fit at the time the therapy is started. Transient cytopenias during repeated chemotherapy courses should not be considered as interrupting durability of response, as long as they recover to the improved counts of the previous course.

Hematologic Improvement

Category	Participant pre-trial baseline	Response criteria
----------	--------------------------------	-------------------

Erythroid response (HI-E)	No Transfusion Dependence at baseline (0 RBC transfusions in 16 weeks)	At least 2 consecutive Hgb measurements ≥ 1.5 g/dL for a period of minimum 8 weeks in an observation period of 16 to 24 weeks compared with the lowest mean of 2 Hgb measurements (apart from any transfusion) within 16 weeks before treatment onset; only a response duration of at least 16 weeks, however, is considered clinically meaningful
	Low Transfusion Dependence at baseline (3-7 RBC transfusions in 16 weeks in at least 2 transfusion episodes, maximum 3 in 8 weeks)	Transfusion independence, defined by the absence of any transfusions for at least 8 weeks in an observation period of 16-24 weeks with the same transfusion policy compared with 16 weeks prior to treatment; only a response duration of at least 16 weeks, however, is considered clinically meaningful

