10.4.3 Analysis of the Secondary Endpoint(s)

- The secondary objectives for phase I are to describe pharmacokinetic properties of BMS-986253 in MDS participants and to evaluate safety and tolerability of BMS-986253 in MDS participants. The AUC, half-life, and Css of BMS-986253 will be evaluated in participants, separately by dose level and cohort using descriptive statistics.
- The secondary objectives for phase II are:
 - (a) to evaluate the safety and tolerability of the agent as measured by the grades and types of toxicity noted for the agent at each dose level, separately by cohort; and,
 - (b) to evaluate efficacy, as measured by clinical outcomes, including OIR (CR + PR + HI + marrow CR + SD), cytogenetic response rate, time to best response, disease free survival (DFS; definition: time to relapse for participants who achieve CR), progression free survival (PFS; definition: disease progression or death from MDS), leukemia free survival (LFS; definition: progression to AML or death from any cause), and overall survival (OS; definition: death from any cause).
 - OIR and cytogenetic response rate will each be reported as a fraction, separately by cohort, along with a 95% confidence interval. Time to best response, DFS,

PFS, LFS, and OS will be evaluated separately for each phase II cohort using the Kaplan-Meier method. In each case, the median time to event will be reported along with a 95% confidence interval for the median.

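### PFS events after the first follow-up call cannot be verified against section 6.3.1 in participants who stop therapy without progression, because outside records are requested only once

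*Combined protocol and SAP*

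**What the plan says.** Section 3.4 (Follow-up) sets the off-therapy schedule: "After the End of Treatment visit, follow up will occur via phone call every 3 months (+/- 1 month) for first 24 months". The interval later widens to half-yearly, give or take 3 months, for a minimum of 5 years from enrollment. On source documents the section says: "Outside medical records will be requested along with the phone call for the first follow-up visit only". Study calendar footnote l (section 3.6) repeats the records limit. The item collected at these calls is "Overall survival, event- and progression-free survival status". End-of-study status is also taken by phone.

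Section 6.3.1 gives the endpoint as "PFS: disease progression or death from MDS". Progression means a rise in marrow blasts past stated thresholds or any of three peripheral criteria: "At least 50% decrement from maximum remission/response in granulocytes or platelets", a hemoglobin fall of 2 g/dL or more, or transfusion dependence. Relapse after CR or PR uses similar measurements. Section 10.4.3 analyzes PFS, DFS and LFS by Kaplan-Meier within each phase II cohort, with a median and 95% confidence interval. It gives no rule for dating events or for censoring.

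Appendix F adds follow-up fields: whether MDS has progressed, into what and when; whether secondary AML has been diagnosed, with month and year; and later MDS or AML treatment where known. Relapse after CR is listed neither there nor among the section 3.4 follow-up items.

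**The concern.** On treatment, progression is sought with a CBC on days 1 and 15 of every cycle and, in phase II, marrows after cycles 2 and 6. If it is found on treatment at the NIH, section 3.4 requires a marrow. Once treatment ends, the definition stays the same but the measurements behind it stop being collected. The End of Treatment visit has a CBC and a transfusion assessment but no required marrow. After the first call the plan requires no blood count, transfusion record or pathology report.

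A participant who stops therapy without progression is still at risk for PFS. A hemoglobin fall or a rise in blasts can go unnoticed by that participant, or be reported long after it happened. With no censoring rule, a call that reports no progression could extend event-free time without any blood count behind it. Both routes lengthen PFS. At stake is the credibility of the PFS medians, and of DFS in the few complete responders who stop early.

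**Working it through.** The documents give no event count, power or expected median for PFS, DFS or LFS, so there is no plan figure to reproduce. The check sets the schedule against the definitions and then sizes the unverified part of follow-up.

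**1. Data needed against data required after the first call**

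| Endpoint | Needs | Required after the first call |
|---|---|---|
| PFS (6.3.1) | Blasts, granulocytes or platelets, Hgb, transfusion dependence; or death from MDS | Reported status and date |
| DFS (10.4.3; relapse in 6.3.1) | Blasts, granulocytes or platelets, Hgb or transfusion dependence, after CR | Relapse not listed |
| LFS (10.4.3) | AML diagnosis or death from any cause | Reported AML, month and year; death |
| OS | Death | Death and its date |

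PFS has the largest gap. LFS lacks only a record confirming the AML diagnosis.

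**2. Number of calls.** Calls every 3 months to month 24 give 24/3 = 8. Calls every 6 months then follow.
- Counting 60 months from the End of Treatment visit: months 30, 36, 42, 48, 54 and 60, so 8 + 6 = 14.
- Counting 5 years from enrollment, with treatment ending after 6 cycles and the visit about 1 month later: 6 × 28/30.44 + 1 = 6.5 months, leaving 60 − 6.5 = 53.5 months. Calls at 30, 36, 42 and 48 give 8 + 4 = 12.

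Records are requested at one call, so 11 of 12 (92%) to 13 of 14 (93%) have none. Sections 3.1 and 10.1 also mention 8 years; a longer period would add calls without records.

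**3. Gaps between calls.** Using the stated windows, consecutive calls can be 3 + 1 + 1 = 5 months apart in the first 24 months and 6 + 3 + 3 = 12 months apart later.

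**4. Share of off-therapy events after the first call (illustration).** Assume exponential time to event from the End of Treatment visit with median m, S(t) = 0.5^(t/m), and follow-up to T = 53.5 months. With the first call at t1:

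share = (S(t1) − S(T)) / (1 − S(T))

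For m = 12 and t1 = 3: S(3) = 0.841 and S(53.5) = 0.046, so the share is (0.841 − 0.046)/(1 − 0.046) = 0.833.

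| Assumed m (months) | First call at month 3 | First call at month 4 to month 2 |
|---|---|---|
| 3 | 50% | 40% to 63% |
| 6 | 71% | 63% to 79% |
| 12 | 83% | 78% to 89% |
| 18 | 88% | 84% to 92% |

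Most off-therapy events fall after the only records request unless the off-therapy median is about 3 months or less. These medians are assumptions. The shares say how many events would lack records, not how many would be missed or by how much median PFS would shift.

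**5. Who is exposed.** Sections 3.1 and 3.8.1 end therapy at C7D1 when there is no clinical response. Section 6.3 says that participants with ECOG 0-2 who reach PR, stable disease or hematologic improvement may receive further therapy. The passages conflict for stable disease and must be reconciled, so the number who stop without progression cannot be fixed from the documents. Toxicity, participant request and investigator discretion (3.8.1) add others.

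**The case against.** The strongest reply is that the gap is narrow and the endpoints are descriptive. Several parts of it stand.

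- A reader might infer that off-therapy events cannot be dated. Appendix F contradicts this: progression and AML dates are collected. What is missing is the source record behind them.
- A reader might infer that DFS and LFS suffer as much as PFS. DFS concerns complete responders, and section 3.1 keeps responders on therapy until progression, death or unacceptable toxicity, so most relapses should be seen on treatment. LFS needs no Hgb, neutrophil, platelet or transfusion data, and an AML diagnosis is something a call can pick up.
- A reader might take one minus the planning response rates of section 10.2 (20% to 50%) and conclude that 50% to 80% of participants leave at C7D1 still at risk. The documents do not support this. Early progressors already have their event. Hematologic improvement alone is outside the section 10.2 response definition but may count as clinical response. Section 6.3 also conflicts with the C7D1 rule for stable disease.
- Transfusion dependence is known to the participant, so not every criterion is hidden from a call. The count-decrement criterion is measured from best response and so mainly concerns responders.
- Section 3.5.1 mentions medical history in long-term follow-up for safety and efficacy, and section 3.8 a safety visit about 100 days after the last dose. Neither specifies counts, marrow or records.
- PFS is a single-arm secondary endpoint without a hypothesis test, and section 10.2 names OS the most important secondary endpoint.

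These points limit the reach and weight of the concern. None supplies a data source for blasts, counts or hemoglobin after the first call in a participant who stopped without progression.

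**Conclusion.** The concern holds for PFS in participants who stop therapy without progression, and for the few off-therapy relapses in complete responders. After the first call, these events cannot be verified against section 6.3.1, and their dates rest on report. Missed or late-dated progression would bias PFS upward. The amount is unquantified, because the documents give neither a missed-event rate nor an off-therapy median, and the number exposed depends on reconciling sections 3.1 and 3.8.1 with section 6.3. The 71% to 88% range rests on assumed exponential medians of 6 to 18 months and a first call at month 3, and is not an estimate of bias. LFS is less exposed, OS is little affected, and the phase II ORR and both two-stage decisions are unaffected. The change is worth making because it is cheap; it is not a condition for the primary objective.

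**What to change.** In section 3.4 and calendar footnote l, replace the limit to the first follow-up visit with a records request at each scheduled contact until progression, AML or death. The request should cover CBCs, transfusions, marrow and pathology reports, and new MDS or AML therapy since the last contact. At minimum, request records whenever progression, relapse, AML or new therapy is reported, and at the last contact. This lighter version leaves unnoticed laboratory progression undetected for longer.

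Add relapse after CR to the follow-up items in section 3.4 and Appendix F.

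In section 10.4.3, state that:
- PFS and DFS events are dated by the first record that meets section 6.3.1 (for PFS, or by death from MDS if earlier);
- LFS is dated by the documented AML diagnosis or death;
- PFS and DFS are censored at the last record showing no event, not at the last call.

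Reconcile sections 3.1 and 3.8.1 with section 6.3 on who leaves therapy after 6 cycles.

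The cost is modest coordinator time: up to 12 to 14 requests per participant instead of one, all at calls already scheduled, with no added visit or procedure. The downside is earlier censoring where records cannot be obtained.

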3.5 ON STUDY ASSESSMENTS/EVALUATIONS

The timepoints for assessments are listed in Section **0**, Study Calendar. Unless otherwise indicated, assessments on dosing days must be performed prior to the administration of study therapy. For screening procedure details, refer to section **2.2**. Baseline evaluations do not need to be repeated if already performed at screening within 8 days prior to initiation of study therapy.

3.5.1 Safety Assessments and Other Assessments

- Physical exam - review of organ systems, weight, and vital signs (i.e., temperature, pulse, respirations, blood pressure). Height will only be required prior to treatment no later than cycle 1 day 1. After initiation of study drug, symptom-directed physical examinations will be performed as clinically indicated in the investigator's judgment.
- Medical history – performed during long term follow up in order to assess safety and efficacy.
- Concomitant medications – a record of all medications including herbal supplements but not including study therapy that a participant has taken during the study will be recorded in order to assess confounding factors in safety and efficacy assessments
- Adverse events – participant reported adverse events will be collected throughout the study in order to assess safety.
- ECOG performance status: an assessment of activities of daily living
- Bone marrow biopsy and aspiration: required at screening/baseline, Phase I post cycle 1(C1D28 +/- 3 days) and Phase II post cycle 2 (C2D28 +/- 3 days) and post cycle 6 (C6D28 +/- 3days); and if needed clinically in the setting of aplasia or concern for disease progression
- Electrocardiogram 12-lead ECGs will be performed at baseline only for safety
- Blood chemistries - Sodium (Na), Potassium (K), Chloride (Cl), Total CO₂ (bicarbonate), Creatinine, Glucose, Urea nitrogen (BUN), Albumin, Calcium total, Magnesium total (Mg), Inorganic Phosphorus, Alkaline Phosphatase, ALT/GPT, AST/GOT, Total Bilirubin, Direct Bilirubin, Total Protein will be performed to assess organ function

- CBC with differential includes Neutrophils, Lymphocytes, Monocytes, Eosinophils, Basophils, WBC, RBC, Hemoglobin, Hematocrit, RBC Indices, MCV, RDW, Platelet.
- TBNK for research
- Other blood test: amylase lipase, creatine kinase, ACTH, TSH, free T4, PT, PTT, INR, ESR and CRP will be performed per study calendar to assess organ function
- Urinalysis for safety
- Serum or urine pregnancy test – performed prior to administration of study therapy in women of childbearing potential and women < 12 months since the onset of menopause to ensure participant is not pregnant

